The teams at Baycrest and JSLG will follow a similar protocol (for both users and informal caregivers) and will submit applications for ethics approval through the Baycrest Research Ethics Board and UCSF Institutional Review Board and the JSLG Research Committee.

Key Outcomes

Users

The key outcome measures of interest are the UCLA Loneliness Scale version 3,¹⁶ Duke's Social Support Index,¹⁷ and the Personal Health Questionnaire (PHQ-8).¹⁹ These outcomes will be measured at enrollment, week 9, and week 18.

Informal Caregivers

The primary outcome for informal caregivers will be their qualitative experiences, as discussed during a focus group or interview session. The evaluated impacts will be caregivers' experiences with the use of the ElliQ messaging function, the perceived changes (if any) on communication strategies between caregivers and their study partner (i.e., the ElliQ users), the perceived changes (if any) in the caregiver's ability to provide care for their study partner, and the perceived changes (if any) to the ElliQ user's social engagement, loneliness, well-being, and access to and use of technology.

Sample Size

Users

According to Russell¹⁶ the mean and standard deviation of the UCLA Loneliness version 3 score for a general older adult population is 31.51 and 6.92, respectively. Assumptions for the sample size calculation include a 2x2 factorial design to anticipate potential site differences, a 5.0-point mean difference in the mean change in the UCLA Loneliness Scale version 3 score between the ElliQ intervention and waitlist control groups, and a standard deviation of 15.0 to account for a 2x higher variability compared to Russell's (1996) reported value. For a mean difference of 5.0 and a standard deviation of 15.0, a medium effect size of 0.33 was used to obtain the required sample size.

Using the PASS 16 sample size calculator, a total sample size of 76 (38 per intervention group, 19 per cell in a 2x2 factorial design) achieves 81% power when F tests are used to test the intervention factor (ElliQ versus Waitlist control), site factor (Baycrest versus JSLG), and intervention–site interaction at a 5% significance level and an effect size of 0.33. It is recommended that the ElliQ study recruit a total of 96 participants (48 per intervention group, 24 per cell in a 2x2 factorial design, Table 1) with a contingency of up to a 20% dropout rate (20 expected dropouts).

Table 1. Number of participants to recruit

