- Is willing and able to use Twilio Messenger to access the ElliQ messaging function
- Understands and abides by the terms and conditions of the messaging app (i.e., Twilio messenger) that links to the ElliQ system
- Is able to speak clearly and in oral English
- Able to hear audio and see and read content on a screen

Exclusion Criteria (Informal Caregivers):

- Individuals who are not an informal caregiver to an ElliQ study participant
- Lives in the same home as the ElliQ study participant
- Does not have access to an Android Smartphone or iPhone running iOS v. 10 or above through which to access Twilio Messenger
- Is unable or unwilling to use Twilio Messenger to access the ElliQ messaging function
- Refuses to abide by the terms and conditions of Twilio Messenger
- Is unable to speak or read in English
- Is unable to hear audio or see/read content on a screen

Randomization

Users

Once participants have been screened, deemed eligible for the study, completed the informed consent process, and have completed the preliminary baseline measures, they will be randomly assigned to either the active condition or a waitlist control group. Stratified randomization with allocation concealment will be implemented in the study. Separate randomization schedules containing unique three-digit numbers with corresponding 1:1 intervention allocation will be generated by a biostatistician at Baycrest using SAS 9.4. Each site (Baycrest and JSLG) will receive randomization schedules for up to 50 participants. The point persons at Baycrest and JSLG will obtain the randomization schedule for their respective sites. The point person(s) at each site will prepare 50 opaque sealed envelopes each containing a unique three-digit number from their site-specific randomization schedule and will give these envelopes to the recruiting research assistants. Once an eligible individual consents to participate in the study, the recruiting research assistant will pick a sealed envelope and use the three-digit number as the consenting participant's study ID. The recruiting research assistant must coordinate promptly with the point person in charge of keeping the randomization schedule to determine the intervention allocation assigned to the specific three-digit number obtained. The research assistant will then inform the consenting and eligible participant regarding their intervention group assignment and proceed with the next steps of study implementation.

ElliQ Implementation

Users

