Those informal caregivers who enroll in the study will attend a baseline session of up to 1 hour immediately after the informed consent process. At this session, informal caregivers will be trained on how to access and use Twilio Messenger as part of the ElliQ messaging function. They will be instructed to use the function for as long as they feel comfortable and willing to do so for the duration of their study partner's 2-month ElliQ test/use period. Informal caregivers will be provided with study staff's contact information, should they have any questions about the device or the study. They will also be informed that they can take as much time as they need to review Twilio's terms of service and privacy statement before agreeing to use the messaging function (where messaging data will be captured and stored by Twilio and not collected, accessed, or used for study purposes).

Data Collection

Users

The following data will be collected as part of the study.

Time 1 (Baseline and Participant Characterization)

Medical/Study Data

- Participant characterization
 - a) Demographics questionnaire
 - b) SF-12¹²
 - c) Lawton's IADL Scale¹³
 - d) Mini-Mental State Examination (MMSE)¹⁴
 - e) Caregiver status questions
- Access to technology/technology literacy
 - a) Computer Proficiency Questionnaire¹⁵
- Loneliness and social isolation
 - a) UCLA Loneliness V3 Scale¹⁶
 - b) Duke's Social Support Scale¹⁷
- Quality of life
 - a) OPQOL¹⁸
- Mood
 - a) Personal Health Questionnaire (PHQ)-8¹⁹
 - b) Visual Analog Mood Scale (VAMS)²⁰
 - c) Brief Mood Introspection Scale (BMIS)²¹

During the Study Period

Product Usage Data (Captured by ElliQ)

The ElliQ system is capable of capturing data on its own, as per its commercially available functions. There are two primary types of data that the ElliQ system can capture; for example:

Product Usage Data – Metrics

- Number of proactive plans initiated by the ElliQ system (e.g., when the ElliQ system initiates small talk or suggests an activity)
- Number of reactive plans (i.e., ElliQ responding to the user)

- Plan context (proactive or reactive)
- Plan type (video, small talk, other)
- Total number of plans per time unit
- Time and date of plan
- The time the device is turned on or off

Product Usage Data – Personal Interactions

- Facial recognition
- IP address
- Speech intent (mapped to ElliQ’s library of intent types)
- TextHeard (speech-to-text data)

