Baseline characteristics of the participants in the two intervention groups will be summarized by site through descriptive statistics, frequencies, or proportions. Comparisons between intervention groups and between sites will be performed to determine whether a balance between intervention groups has been achieved as a result of the randomization process conducted at the site level. Analyses will include independent *t*-tests for continuous data or chi-squared tests for proportions. If the distribution of any continuous measure is markedly skewed or contingency tables for proportions contain cell sizes <5, non-parametric tests, namely the Mann–Whitney U/Wilcoxon rank-sum test and Fisher's exact test, will be conducted in place of the independent *t*-test and chi-squared test, respectively.

Primary Analysis (Users)

Analysis of the effect of the intervention on the key outcome measures will be performed using an intent-to-treat approach, thus including all randomized participants. The primary analysis will include participants in the ElliQ intervention group and the comparable contemporary waitlist control. If there is balance in participants' characteristics across the two sites, evaluation of changes in the outcomes will only include the intervention as the independent variable of interest. In this case, the mean change in the outcome scores from Baseline to Post 1 (Session 2) will be calculated for each intervention group. The calculated mean change will be compared between intervention groups using an independent *t*-test. Effect sizes within an intervention group (standardized response means) and between groups will be calculated to measure the magnitude of mean differences. In the case of an imbalance between sites, the primary analysis will be a linear regression model involving the change in primary outcome as a function of intervention, site, and intervention–site interaction. Measurements of the primary outcome obtained at Time 3 for the ElliQ intervention group and on the waitlist control after being given ElliQ will not be included in this primary analysis.

Sub-Analyses (Users and Informal Caregivers)

Sub-analyses will involve the assessment of the outcomes when participants are exposed to ElliQ and evaluating differences in the trends in bi-weekly engagement survey responses between intervention groups.

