To evaluate the change in the outcomes before and after exposure to ElliQ, outcome measurements obtained from the ElliQ intervention group at Baseline and Time 2 will be pooled with the measurements obtained from the waitlist control group before (Time 2) and after (Time 3) exposure to ElliQ. Change analysis will be conducted through the paired *t*-test and standardized response mean.

To assess sustained impact of ElliQ on the outcomes, the trajectory of the primary outcome from baseline, post, and follow-up within the ElliQ intervention group will be evaluated through a linear mixed-effects model with a random intercept to account for the intra-individual variability in repeated measurements per participant. The model will involve the primary outcome and time as the independent variable, which will be treated as a factor with three levels representing the three time points.

To determine the difference in the trend of bi-weekly engagement survey responses between intervention groups, a linear mixed-effects model with a random intercept for the scaled response as a function of time, intervention, and time-intervention interaction will be performed.

Level of significance for the statistical tests will be set at 0.05 and analyses will be carried out using SAS 9.4.

Qualitative analysis

Where possible, focus groups with up to 6–8 participants at a time will be scheduled with study participants (users and informal caregivers) at week 9 (intervention group) or week 18 (waitlist control group). Where a focus group session is not feasible (either due to participant's schedules or preferences), individual interviews will be held instead. Those informal caregivers who are unable to attend an in-person session may be invited to an audio-recorded telephone interview. The focus groups/interviews will be facilitated by research staff, and a semi-structured interview guide will be used. The questions may be modified based on the nature of the discussion that emerges during the session, but any additional questions will remain topical and will explore participants' experiences with ElliQ across numerous domains.

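### The primary model is picked by an undefined check of baseline balance between sites, although site is the randomization stratum and can be in the model in every case

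*Combined protocol and SAP*

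**What the plan says.** The Primary Analysis (Users) section sets out two models. The first applies when the sites are judged similar, and the text for that case runs: "characteristics across the two sites, evaluation of changes in the outcomes will only include the intervention as the independent variable of interest". Mean change from Baseline to Session 2 is then compared by an independent t-test. The alternative reads: "In the case of an imbalance between sites, the primary analysis will be a linear regression model involving the change in primary outcome", with intervention, site and intervention-by-site interaction as terms.

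Four other places bear on this:

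- **Randomization (Users):** "Stratified randomization with allocation concealment will be implemented in the study". Site is the only stratum that can be identified: "Each site (Baycrest and JSLG) will receive randomization schedules for up to 50 participants", with 1:1 allocation.
- **Sample Size (Users):** "Assumptions for the sample size calculation include a 2x2 factorial design to anticipate potential site differences". The 81% power with 76 participants (19 per cell) is for F tests of intervention, site and interaction.
- **Participant characterization, under Data Analysis:** "Comparisons between intervention groups and between sites will be performed", using t-tests, chi-squared tests or their non-parametric counterparts. The stated purpose is to check balance between the intervention groups.
- **End of Sub-Analyses:** "Level of significance for the statistical tests will be set at 0.05".

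The baseline measures are listed in Data Collection under "Time 1 (Baseline and Participant Characterization"). Five instruments are labelled characterization, and seven more cover technology, loneliness, quality of life and mood.

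**The concern.** There are three problems.

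1. **The trigger does not answer the relevant question.** With a separate 1:1 schedule per site, the arms are comparable within each site however different the sites are. A site difference therefore does not confound the arm comparison and is not a reason to add site. Conversely, sites that look alike at baseline may still differ in mean change, so similarity is not a reason to drop site. The sample size was also computed for a design that contains site.

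2. **The switch has no decision rule.** The tests and a 0.05 level are named, but nothing says which characteristics count, whether one result below 0.05 is an imbalance, or what follows when some items differ and others do not. Two analysts could follow the text and run different primary analyses.

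3. **The branches differ in more than site.** The t-test branch omits the stratification factor. The regression branch includes an interaction without saying which contrast is the primary effect. If site is reference-coded, the intervention coefficient is the effect at one site only.

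At stake are a primary model that is not fixed before baseline data are seen, and some lost precision.

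**Working it through.** **Inputs.** From Sample Size: 76 evaluable, 38 per arm, 19 per cell, SD 15, mean difference 5.0, effect size 0.33. From Sub-Analyses: significance level 0.05, taken as two-sided. The documents give no site difference in mean change, so 5, 10 and 15 points are assumed as a range.

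**The plan's own figure.** Power of a 1-df F test with noncentrality N × f² = 76 × 0.33² = 8.28 and 72 error df is 0.810, which reproduces the stated 81%. This treats 0.33 as Cohen's f, which corresponds to a difference of 2 × 0.33 × 15 = 9.9 points. But 5.0/15.0 = 0.33 is a standardized difference d, so f is 0.167, the noncentrality is 76/36 = 2.11, and power is 0.30. Both readings are carried below.

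**Cost of always including site, if the sites do not differ in change.** The standard error of the difference is 15 × √(2/38) = 3.44.

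| Model | Error df | Power at 5.0 points | Power at 9.9 points |
|---|---|---|---|
| t-test, no site | 74 | 0.2998 | 0.8104 |
| intervention + site | 73 | 0.2998 | 0.8103 |
| with interaction, site-averaged effect | 72 | 0.2997 | 0.8101 |

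The cost is below 0.1 percentage point.

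**Cost of leaving site out, if the sites differ in change by D.** With balanced cells, the t-test's pooled variance has expectation 225 + 38 × (D/2)²/37:

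- D = 5: 231.4, SE ratio √(231.4/225) = 1.014
- D = 10: 250.7, SE ratio 1.056
- D = 15: 282.8, SE ratio 1.121

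The true sampling error of the arm difference does not change, because each site contributes equally to both arms. The t-test therefore overstates the standard error. Simulation with 1,000,000 runs per setting and 19 per cell gives:

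| D | Type I error, no site | Type I error, with site | Power at 5.0, no site / with site | Power at 9.9, no site / with site |
|---|---|---|---|---|
| 5 | 4.7% | 5.0% | 29% / 30% | 80% / 81% |
| 10 | 3.9% | 5.0% | 26% / 30% | 78% / 81% |
| 15 | 2.8% | 5.0% | 22% / 30% | 74% / 81% |

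**How often the switch would fire by chance.** Suppose any baseline test with p < 0.05 counts as imbalance, the sites truly do not differ, and the tests are independent. The chance of being sent to the regression is 1 − 0.95^k: 5% for k = 1, 23% for k = 5, 40% for k = 10 and 54% for k = 15. The plan gives no k.

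**The two-stage procedure itself.** Take k = 10, let the balance result be independent of the outcome, and read the regression as the site-averaged effect (20,000 runs per setting). Type I error is 4.9%, 4.3% and 3.8% at D = 5, 10 and 15, and power at 9.9 points is 81%, 79% and 77%. It lies between the two models and is not inflated.

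**The interaction branch.** If the reference-coded coefficient is taken as primary, only one site informs it and the noncentrality halves. Power falls from 81% to 52% at 9.9 points and from 30% to 17% at 5.0 points.

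**The case against.** The best defence is that both branches are written down in advance, and that the trigger uses participants' characteristics across sites, not Time 2 outcomes or the arm contrast. As written, it gives no direct route to the model that favours ElliQ. That is fair, and the calculations show no inflation of type I error. But a conditional plan is fixed only when its condition is defined, and this one is not.

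A reader could also infer p < 0.05 from the named tests and the overall level. That is a natural reading. It still leaves mixed results across several characteristics unresolved, and the stated purpose of those tests is balance between arms, whereas the switch turns on balance between sites.

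The conservatism of the t-test depends on nearly equal arms within each site. The plan states no block size, and some participants will drop out. With 96 randomized and 20% random dropout, type I error is about 4.8%, 4.1% and 3.3% from 24 per cell, and about 5.0% throughout under unrestricted 1:1 allocation. So the type I figures above are specific to balanced cells, which Table 1 and the per-site schedules suggest. The loss of power at 9.9 points persists under all these allocations.

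Finally, the larger losses need a site difference in change of 10 to 15 points, two to three times the stated treatment effect, and nothing in the documents suggests one. This stands, and it limits the size of the concern.

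**Conclusion.** The concern holds. The primary model turns on a between-site comparison that is undefined and does not show whether site is related to change, and one branch drops the randomization stratum. The t-test branch is valid; its weakness is conservatism and lost precision if the sites differ in change.

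The quantified harm is modest. It is nil with no site difference, about one percentage point of power at a 5-point site difference, and about 7 to 8 points at a 15-point difference. These figures assume 19 per cell, SD 15 and site differences that the documents do not supply. The stronger reason to act is that the primary analysis is left open to interpretation, both in the choice of branch and in the contrast to be read from the interaction model, when a nearly free remedy exists. The change should be made, but the trial's validity does not depend on it.

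**What to change.** In Primary Analysis (Users), delete the balance condition and specify one model for all cases: change from Baseline to Time 2 on intervention plus site, with the intervention main effect as the primary contrast. Put the intervention-by-site interaction and the site-specific estimates in a named secondary model. In Participant characterization, keep the arm and site comparisons descriptive and state that they play no part in choosing the model.

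In Sample Size (Users), name the intervention main effect of this model as the powered test, in place of the joint reference to intervention, site and interaction, and state whether 0.33 is d or Cohen's f.

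An interaction model with the site-averaged effect as its named primary contrast would also remove the switch, at equal power. The additive model is simpler and avoids the coding ambiguity.

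The cost is a few sentences in three places and one degree of freedom. No new data are needed, and the change itself calls for no increase in sample size.

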Those who get assigned to the second (waitlist) condition will attend an initial baseline data-collection session (time 1; week 0), where questionnaires related to participant characteristics and baseline measures will be administered. Participants will then wait for 8 weeks to get the ElliQ device (weeks 1–8). After this 8-week wait, participants will be invited to attend another data-collection session (time 2; week 9), where they will be asked to complete some of the same measures that they completed at time 1. Following this session, participants will trial the device for 8 weeks (weeks 10–17). After the 8-week trial, participants will be asked to attend a post-trial data-collection session (time 3; week 18), where they will return the ElliQ system. Participants will then complete a number of the same measures that were completed at times 1 and 2, and attend a one-time, audio-recorded focus group or interview session, where field notes will be taken.

Upon completion of the study tasks (i.e., at the final data-collection session at week 18), each participant's study participation will conclude.

Informal Caregivers

Informal caregivers (e.g., family, friends who provide care for the ElliQ user) may also be enrolled in the study to investigate their experiences with the messaging function of the ElliQ system (user and caregiver pairs will be referred to as “dyads” going forward). Of note, users who do not have caregivers can still enroll in the study.

This will be an exploratory study, insofar as eligible and consented informal caregivers will complete a baseline data collection session for participant characterization; they will also have the opportunity to test the ElliQ messaging function for the 2 months while their study partner (i.e., the ElliQ user) tests the ElliQ system. Informal caregivers will have the opportunity to discuss their ElliQ experience, caregiving experience, and their perception of the impacts the ElliQ system and messaging function had on their study partner's social engagement, loneliness, access to technology, and use of different communication methods (e.g., online, in-person, over the phone, etc.). An audio-recorded focus group or interview (where field notes will be taken) will be held with informal caregivers at the end of the ElliQ users' 2-month test/use period (i.e., on or around week 9 for caregivers of users in the intervention group, or on or around week 18 for caregivers of users in the waitlist control group).

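### Both versions of the primary analysis compare change scores and leave out the baseline score, which costs precision that adjustment would usually recover at no extra data

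*Combined protocol and SAP*

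**What the plan says.** The Primary Analysis (Users) section has two branches, chosen by whether participant characteristics are balanced across sites.

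- **Sites balanced:** "the mean change in the outcome scores from Baseline to Post 1 (Session 2) will be calculated for each intervention group", and "The calculated mean change will be compared between intervention groups using an independent" *t*-test. Intervention is the only explanatory variable.
- **Sites imbalanced:** "a linear regression model involving the change in primary outcome as a function of intervention, site, and intervention–site interaction".

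Neither branch contains the baseline score. The Sub-Analyses section does not supply it either: it covers a pooled before-and-after comparison, a within-arm trajectory and the engagement survey.

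The scores exist. Key Outcomes names the UCLA, Duke and PHQ-8 scales and says "These outcomes will be measured at enrollment, week 9, and week 18". Data Collection lists all three under "Time 1 (Baseline and Participant Characterization").

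The order of baseline scoring and allocation is described in three ways. Randomization (Users) says that participants who "have completed the preliminary baseline measures, they will be randomly assigned to either the active condition or a waitlist control group", without defining those preliminary measures. The envelope procedure in the same section reads "Once an eligible individual consents to participate in the study, the recruiting research assistant will pick a sealed envelope" and goes on to disclosure of the allocation without mentioning baseline. Study Design says "Those who get assigned to the second (waitlist) condition will attend an initial baseline data-collection session (time 1; week 0").

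**The concern.** A change score subtracts the baseline value with its coefficient fixed at 1. The best-fitting coefficient is r times the SD ratio, which is usually below 1. The subtraction then over-corrects: an arm that by chance starts lonelier will tend to show more improvement whether or not the device works. Over repeated randomisations this averages out, so there is no bias, but it adds noise to the treatment estimate. Analysis of covariance estimates the coefficient and removes that noise.

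The trial plans on 38 completers per arm, so avoidable noise matters, and the covariate is already being collected. The plan also tests baseline balance between arms, yet only imbalance between sites changes the model. A chance difference between arms in starting loneliness would lead to no adjustment.

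Timing matters to both methods. If some participants gave baseline answers after learning their group, those answers could be affected by that knowledge, and the change score and the covariate would both suffer.

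**Working it through.** **Inputs from the document (Sample Size, Users):** 76 completers, 38 per arm; target difference in mean change 5.0 points; SD 15.0; cited SD of a single UCLA score 6.92; 5% significance level.

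**Assumed, because the document gives neither:** r, the baseline-to-week-9 correlation, from 0.5 to 0.9; and k = week-9 SD / baseline SD, from 0.8 to 1.2.

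**The plan's own figure.** A noncentral F test with 1 and 72 degrees of freedom and noncentrality 76 × 0.33² = 8.28 gives power 0.810, matching the stated 81%. This requires 0.33 to be entered as Cohen's f. But 5.0/15.0 is a standardised difference d, so f is half of it, 0.167, and power is 30%. That is a separate issue, but it sets the scale for what follows.

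**Variance comparison.** With baseline SD s:

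- Var(change) = s²(1 + k² − 2rk)
- Var(baseline-adjusted residual) = s²k²(1 − r²)
- Large-sample gain = (1 − rk)² / (1 + k² − 2rk), which is (1 − r)/2 when k = 1 and zero when rk = 1
- Estimating the slope with site in the model multiplies the adjusted variance by 1 + 1/71

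Example, k = 1 and r = 0.5: the ratio is 0.75/1.00 = 0.75. With the slope cost it is 0.75 × 72/71 = 0.761, a net gain of 23.9%. This is like having 76/0.761 = 100 completers.

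Net change in variance with 76 completers (plus sign = gain in precision):

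| k | r = 0.5 | r = 0.7 | r = 0.8 | r = 0.9 |
|---|---|---|---|---|
| 0.8 | +42.1% | +36.3% | +35.1% | +38.3% |
| 1.0 | +23.9% | +13.8% | +8.7% | +3.7% |
| 1.2 | +11.7% | +2.0% | −1.1% | +0.9% |

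At k = 1.0 the equivalent numbers of completers are 100, 88, 83 and 79 instead of 76. The loss can never exceed the slope cost, 1/71 = 1.4%, which is reached when rk = 1.

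**Simulation check** (40,000 null trials per cell, baseline and site in the model). The variance ratios, adjusted over change, at k = 1.0 are 0.75, 0.86, 0.91 and 0.96, in line with the table. Both estimators average within 0.002 baseline SD of zero. At k = 1.0 the change-score estimate has a slope on the chance baseline difference of −0.51, −0.30, −0.20 and −0.10; for the adjusted estimate it is about 0. This slope is how the variance is lost, not a further harm.

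**In UCLA points** (noncentral *t*, 74 df for the *t*-test and 72 adjusted, k = 1.0). The two readings of the SD are alternatives and cannot both describe this trial.

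*Reading A: 15.0 is the SD of change.* The standard error is 15 × √(2/38) = 3.44.

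| | Change score | Adjusted, r = 0.5 / 0.7 / 0.8 / 0.9 |
|---|---|---|
| 95% CI half-width | 6.9 | 6.0 / 6.4 / 6.6 / 6.7 |
| Power for 5 points | 30% | 38% / 34% / 32% / 31% |

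Adjusted power is 43% to 47% at k = 0.8 and 30% to 33% at k = 1.2.

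*Reading B: 6.92 is the SD of a single score.*

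| r | Half-width, change → adjusted | Power, change → adjusted |
|---|---|---|
| 0.5 | 3.16 → 2.76 | 87.5% → 94.6% |
| 0.7 | 2.45 → 2.28 | 98.0% → 99.1% |
| 0.8 | 2.00 → 1.91 | 99.8% → 99.9% |
| 0.9 | 1.41 → 1.39 | about 100% both ways |

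**The case against.** The strongest reply is that nothing here is an error. A change-score comparison is valid under randomisation, already uses each person's baseline, and matches a sample size framed on mean change. The gain cannot be derived from the document, and at k = 1.2 with r of 0.7 or more it is essentially nil. Adjustment also decides little on power: under reading A power stays below 50% in every case computed, and under reading B it is mostly high already. All of this stands. It fixes the weight of the point as an efficiency recommendation, without removing it, because the possible loss is about 1% and the possible gain many times that.

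Two objections to the scenarios are also fair.

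- Reading A with k = 1.0 implies a single-visit SD of 15/√(2(1 − r)), which is 23.7 at r = 0.8 and 33.5 at r = 0.9. Against a cited mean of 31.51 and SD of 6.92 these are hard to believe.
- A third reading takes 15.0 as the SD of a single score. At k = 1.0 power then goes from 30% to 38%, 46% to 51%, 62% to 66% and 89% to 90% as r rises from 0.5 to 0.9. The gain is again modest and in the same direction.

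The figures in points apply to UCLA only; the document gives no SD or target difference for Duke or PHQ-8.

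On timing, the Study Design sentence may simply describe the waitlist arm's path and need not mean that allocation came first. The envelope steps still omit baseline, and the preliminary measures are undefined, so clarification is warranted. It is a wording point and adds nothing to the size of the loss.

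**Conclusion.** The concern holds. Neither branch of the primary analysis uses the baseline score as a covariate, and no other section adds it. If baseline is scored before allocation is known, the cost is precision and not validity. With equal visit SDs and r between 0.5 and 0.9, both assumed, the variance given up is about 24% down to 4%. For SD ratios of 0.8 to 1.2 the computed range is a 42.1% gain to a 1.1% loss, with a gain in eleven of twelve cells. The benefit is therefore likely but not certain. The omission itself is clear from the text; only the size rests on assumptions. Adjustment should be made, but it should not be presented as a remedy for the sample size.

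**What to change.** Prespecify as the primary analysis, whatever the balance tests show, an analysis of covariance of the Time 2 score (or the change, which gives the same treatment estimate) on intervention, the baseline value of the same score, and site as the randomisation stratum. Apply it to UCLA, Duke and PHQ-8, and report the adjusted mean difference with its 95% CI. Keep the intervention–site interaction as a separate, stated test. Keep mean changes and standardised response means as descriptive output. Reconcile Study Design with the two descriptions in Randomization so that baseline scoring clearly precedes knowledge of allocation.

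The cost is SAP wording, one clarifying sentence on order and one SAS procedure, with no new data or visits. With 76 completers, residual degrees of freedom fall from 74 to 72 against the *t*-test. They are unchanged against the planned regression with site and interaction, which also leaves 76 − 4 = 72.
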